8.1. Primary Efficacy Analysis

The sensitivity and specificity of the blinded independent read of DaTSCAN[™] SPECT images in detecting or excluding SDD, when the clinical diagnosis as established by the investigator is used as the standard of truth, will be summarized with both by-reader and majority-read analyses. Generally, True Positives (TP) include subjects with a clinical diagnosis of PS and having DatSCAN[™] assessment as SDD positive. False Negatives (FN) include subjects with a clinical diagnosis of PS but having DatSCAN[™] assessment as SDD negative. True negatives (TN) include subjects with a clinical diagnosis of ET or HV and having DatSCAN[™] assessment as SDD negative. False Positives (FP) include subjects with a clinical diagnosis of ET or HV but having DatSCAN[™] assessment as SDD positive. The efficacy will be measured by the following and presented by timepoint in the following summary tables:

- Sensitivity: Subjects with a clinical diagnosis of PS will be included. It will be defined as positive percentage agreement and calculated as the number of TP / (number of TP + number of FN): TP/(TP + FN), and a 2-sided 95% binomial confidence interval constructed around it.
- Specificity: Only subjects with a clinical diagnosis of ET will be included, which means that the HVs will be excluded from this analysis. It will be defined as negative percentage agreement and calculated as the number of TN / (number of TN + number of FP): TN/(TN + FP), and a 2-sided 95% binomial confidence interval constructed around it.
- Accuracy: Subjects with clinical diagnosis of PS, ET, and HV will be included. It will be calculated as overall percentage agreement and calculated as (TP + TN) / (TP + FN + TN + FP), and a 2-sided 95% binomial confidence interval constructed around it.

The two primary hypotheses and alternative hypotheses are:

- Sensitivity $\leq 85\%$ vs Sensitivity >0.85
- Specificity $\leq 85\%$ vs Specificity >0.85

The sensitivity will be successfully established for **a reader** if the lower bound of the 1-sided 95% confidence interval of the sensitivity for this reader is > 85%. The sensitivity will be successfully established **for the study**, only if the sensitivity is successfully established for at least two readers. The specificity will be similarly analyzed.

Additional sensitivity and specificity analyses will be performed based on the outcome from the majority read as supportive analyses. In these analyses, only data with valid majority outcomes will be included (i.e., records with a three-way tie will not be included in this analysis.).

8.2. Secondary Efficacy Analysis

A semi-quantitative analysis of the striatal uptake ratios in specific regions of interest (ROIs; including left and right striatum, caudate, and putamen) of DaTSCANTM SPECT images will be performed with DaTQUANTTM. To account for nonspecific binding, the DaTSCANTM uptake in the ROI will be normalised to DaTSCANTM uptake in the subject's occipital cortex. The normalised DaTSCANTM uptake values for each ROI will be summarized with descriptive statistics for each category of subjects with SDD, ET, and HV. For all striatal uptake ratios, an analysis of variance (ANOVA) will be carried out to test for differences in the striatal uptake ratios among the clinical diagnosis groups. A by-subject listing of DaTSCANTM uptake values for each ROI will be provided.

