6 STUDY DESIGN

6.1 Overall Study Design and Plan

This is a multicentre, open-label, non-controlled, non-randomised clinical study to compare the SPECT findings after a single IV administration of DaTSCANTM ioflupane (¹²³I) injection for patients with a clinical diagnosis of PS (SDD; specifically, patients with PD [SDD], MSA [SDD] or PSP [SDD]) as compared with patients with a clinical diagnosis of ET (no SDD) and age-matched healthy controls.

This study will be conducted at approximately 10 centres in China. The planned sample size for this clinical investigation will be 140 evaluable subjects (60 with movement disorder and SDD, 60 with movement disorder but without SDD, 20 HVs). On the basis of a previous study (DP008-003), it is projected that evaluable results will be obtained from 80% of diseased individuals and 90% of HVs. After adjustment for losses, it is therefore expected that 150 patients with movement disorders (with and without SDD) and 22 HVs will be needed to provide the minimum required number of evaluable patients.

Each subject will be required to visit the study centre for a screening visit, baseline visit, DaTSCANTM imaging visit, and 1 follow-up visit. In order to prevent misinterpretations of the DaTSCANTM SPECT images by the independent blinded readers (who will not be supplied with clinical data), the absence of structural abnormalities in the basal ganglia must be ruled out by a magnetic resonance imaging (MRI) scan performed within 6 months prior to inclusion. If an MRI scan is not clinically feasible, cerebral computed tomography (CT) image findings will also be accepted. If the subject does not have an MRI scan, one will be offered (provided no contraindications are met). If an MRI is not feasible, the investigator will consider offering a CT scan.

During the baseline visit, safety assessments and an extensive neurologic examination will be performed. At that visit, each subject will receive a clinical diagnosis (e.g., PD or ET or no neurologic disease).

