6.2 Study Rationale

6.2.1 Justification for the efficacy analysis of diagnosis of PS

PD is characterised by the progressive degeneration of the dopamine-producing neurons in the substantia nigra pars compacta, and the ventral tegmental area [Gibb and Lees 1991], [Bernheimer et al. 1973]. As a result of this neuronal loss, a marked decrease of striatal dopamine content can be detected [Hornykiewicz and Kish 1986]. The dopaminergic nigrostriatal neuron bundle is crucial in the function of the neostriatum (caudate nucleus and putamen) and its control of movement. MSA and PSP also involve progressive degeneration of dopaminergic nigrostriatal neurons that may produce a DaTSCANTM image that is indistinguishable from that of a patient with PD. In contrast, the dopaminergic nigrostriatal bundle is not involved in the aetiology of ET. Nevertheless, patients with ET have often been given a misdiagnosis of PD [Guberman 1994].

The reliability of the clinical diagnosis of PD is approximately 76% [Hughes et al. 1993], [Meara et al. 1999]. Clinical studies have shown that visual assessment of DaTSCANTM SPECT images permits detection of loss of functional dopaminergic nigrostriatal neurons and confirm that DaTSCANTM imaging can discriminate PS from ET. However, it cannot differentiate the different PS subtypes: PD, MS, and PSP.

Longitudinal studies have shown an average age-related decline in DAT availability of 5.5 % per decade both sexes [Varrone et al. 2013], justifying the addition of a group of age-matched controls who will be expected to show some decline in the uptake of DaTSCANTM with no movement disorders.

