7.2 Inclusion Criteria

For all subjects:

1. Chinese male or female, aged 40 to 80 years, has agreed to sign and date the written informed consent form.

For HVs:

2. Non-patient volunteers with good age-appropriate health as established by clinical examination during screening and no evidence of movement disorder by complete neurological evaluation.

For patients with PD:

3. A diagnosis of clinically established or clinically probable PD in accordance with the MDS Clinical Diagnostic Criteria for Parkinson's Disease [Postuma et al. 2015], Appendix 15.1.1.

For patients with MSA (SDD):

4. A diagnosis of probable or possible MSA in accordance with the Second Consensus Statement on the Diagnosis of MSA [Gilman et al. 2008], Appendix 15.1.2.

For patients with PSP (SDD):

5. A diagnosis of probable or possible PSP in accordance with the Clinical Criteria for the Diagnosis of Progressive Supranuclear Palsy National Institute for Neurological Disorders and Society for PSP (NINDS-SPSP) [Litvan et al. 1996], Appendix 15.1.3.

For patients with ET (no SDD)

6. A diagnosis of definite or probable ET in accordance with the Washington Heights-Inwood Genetic Study of Essential Tremor (WHIGET) diagnostic criteria for ET (no SDD) [Louis et al. 1997], Appendix 15.1.4.

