8.2 Method of Numbering Subjects and Assigning Subjects to Treatment Groups

In this open-label study, all subjects will undergo the same procedure: diagnostic imaging with DaTSCANTM ioflupane (¹²³I) injection.

Each subject will be given a unique identification number. The identification number will be assigned to the subject during the screening visit, after the informed consent document has been signed and dated. Once an identification number has been assigned, it cannot be reassigned, even if the subject is deemed ineligible or withdraws consent. No subject may enter the study more than once. Nor may a subject be re-screened for the study after having failed to meet the inclusion/exclusion criteria. If the investigator has any question about any subject's eligibility to participate in the study, the investigator or study personnel should contact the sponsor to discuss the subject's eligibility.

Each subject's identification number will consist of a 3-digit site code plus a 4-digit consecutive number. For example, site "999" will assign the number "999-0001" to its first subject, "999-0002" to its second subject, and so on. To preserve the integrity of the study, it is crucial that these numbers be assigned in consecutive numerical order.

All subjects will receive the same treatment. Therefore, there will be no assignment to treatment groups.

No randomisation will take place in this study. For analysis, the subjects will be assigned to diagnostic categories according to their clinical diagnosis (e.g., PD, MSA, PSP, ET, or HV).

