12.5.2 Secondary efficacy analyses

12.5.2.1 Semi-quantitative analysis

A semi-quantitative analysis of the striatal uptake ratios in specific regions of interest (ROIs; i.e., left and right striatum, caudate, and putamen) of DaTSCANTM SPECT images will be performed with DaTQUANTTM. To account for nonspecific binding, the DaTSCANTM uptake in the ROI will be normalised to DaTSCANTM uptake in the subject's occipital cortex. The normalised DaTSCANTM uptake values for each ROI will be summarised with descriptive statistics for each category of subjects with SDD (PD, MSA, or PSP) and each category of subjects without SDD (ET and HVs). For all striatal uptake ratios, an analysis of variance (ANOVA) will be carried out to test for differences in the striatal uptake ratios among the clinical diagnosis groups.

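### The secondary ANOVA of striatal uptake has no age term, so any mean-age gap between the non-randomised diagnosis groups shifts their estimated differences by about 0.55% of the mean per year

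*SAP*

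**What the plan says.** SAP 8.2 plans, for every uptake ratio, that "an analysis of variance (ANOVA) will be carried out to test for differences in the striatal uptake ratios among the clinical diagnosis groups". Protocol 12.5.2.1 has the same analysis. Neither names a covariate, and SAP 11 declares no departure from the protocol.

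The protocol treats age as relevant to uptake in two places. Section 6.2.1 cites "an average age-related decline in DAT availability of 5.5 % per decade both sexes" and presents this as "justifying the addition of a group of age-matched controls who will be expected to show some decline in the uptake". Section 10.2.3 gives the blinded readers each subject's age because specific uptake falls as age rises.

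On age balance, section 6.1 compares PS with "patients with a clinical diagnosis of ET (no SDD) and age-matched healthy controls". No section gives a matching ratio, age band, quota or check. The one age rule, in section 7.2, is the same for everyone: "Chinese male or female, aged 40 to 80 years". Section 12.7 asks each centre for 2 to 4 HVs without an age condition. The web system in section 7.1 monitors the distribution of recruits but does not name age. Nothing aligns the ages of the PS and ET groups.

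The groups entering the ANOVA are not listed either. SAP 8.2 summarises uptake "for each category of subjects with SDD, ET, and HV", whereas protocol 12.5.2.1 separates PD, MSA and PSP. SAP 4.1 uses PS, ET and HV for the general and safety tables, so three groups is the natural reading.

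**The concern.** The groups are defined by diagnosis, not by randomisation, so their age distributions may differ systematically. A one-way ANOVA attributes any resulting uptake difference to diagnosis. The visual read of a scan is informed by age, but the quantitative comparison of the same scans is not.

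At stake is the size of the between-group differences, which the secondary endpoint is meant to describe. The ET versus HV difference is the most sensitive: no dopaminergic deficit is expected in either group, so a small age effect could be most of what is seen. If HVs were younger than ET patients, ET uptake would look reduced; if older, the reverse. Age is summarised by diagnosis, so an imbalance would be visible, but an adjustment added after seeing it would not be prespecified.

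**Working it through.** The plan gives no expected uptake, SD or effect size for this analysis, and protocol 12.8 says that no secondary variable was powered. There is no planned figure to reproduce, so the check starts from the protocol's slope.

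**Inputs from the documents.** Slope 5.5% per decade (protocol 6.2.1). Evaluable subjects: 60 with PS, 60 with ET, 20 HVs (protocol 6.1, SAP 3.1). Ages 40 to 80 (protocol 7.2).

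**Assumptions.** The slope for transporter availability applies to the uptake ratio. Within-group SD is 15% to 25% of the mean. PS deficit is 30% of the mean. Age SD is 8 years, or 11.55 years if ages are uniform over 40 to 80 (40/√12).

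**1. Shift per year of age gap.** 5.5% / 10 = 0.55% of the mean. The compound form is 1 − 0.945^(gap/10).

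| Mean-age gap | Linear shift | Compound shift |
|---|---|---|
| 2 years | 1.1% | 1.13% |
| 5 years | 2.75% | 2.79% |
| 10 years | 5.5% | 5.50% |

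**2. Shift against the precision of ET versus HV.** The 95% half-width is t(78) × SD × √(1/60 + 1/20) = 1.99 × SD × 0.258. At SD 15%, 20% and 25% it is 7.7%, 10.3% and 12.9% of the mean. A 5-year gap takes 36%, 27% and 21% of it; a 10-year gap takes 71%, 53% and 43%.

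**3. PS versus ET.** The half-widths are narrower, at 5.4%, 7.2% and 9.0%, so the same shift is a larger fraction of them: about 0.3 to 0.5 at 5 years and 0.6 to 1.0 at 10. Against the effect itself it is modest: 2.75/30 = 9% and 5.5/30 = 18% of the assumed deficit.

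**4. Omnibus F test.** With groups of 60/60/20 and the 30% deficit reduced to 24.5% by an offsetting 10-year gap, power from the noncentral F is 1.000, 1.000, 0.9996 and 0.992 at SD 15%, 20%, 25% and 30%.

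**5. Can chance produce the gap?** The SE of a mean-age difference is age SD × √(1/n1 + 1/n2).

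| Age SD | Contrast | SE (years) | Chance of a gap of at least 5 years |
|---|---|---|---|
| 8 | ET–HV | 2.07 | 1.6% |
| 8 | PS–ET | 1.46 | 0.06% |
| 11.55 | ET–HV | 2.98 | 9.4% |
| 11.55 | PS–ET | 2.11 | 1.8% |

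A gap of 5 to 10 years would therefore mostly need a systematic difference in who is recruited.

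**6. Would a single age slope suffice?** Going by its title in protocol section 14, the source cited for the slope is a healthy-control database, so the documents give no slope for PS. A simulation (8,000 trials, SD 20%, age SD 8, PS deficit 30%, HVs younger by 5 or 10 years) gave these ET–HV biases, as a percentage of the mean:

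| True slopes | Model | 5 years | 10 years |
|---|---|---|---|
| Equal in all groups | ANOVA | 2.7 | 5.5 |
| Equal in all groups | ANCOVA, common slope | 0.0 | 0.0 |
| Zero in PS | ANOVA | 2.8 | 5.5 |
| Zero in PS | ANCOVA, common slope | 1.2 | 2.4 |
| Zero in PS | ANCOVA, own PS slope | 0.0 | 0.0 |

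In the zero-slope case a common slope leaves 1.2/2.8 = 43% or 2.4/5.5 = 44% of the bias. That case is an extreme chosen to show the mechanism; no document asserts it.

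**The case against.** The strongest reply is that nothing planned would come out differently. The only test named is an omnibus one, its power stays at 0.99 or above under step 4, and no success criterion uses it. HVs are recruited to build a reference database, and their secondary objective is to assess uptake, which descriptive statistics meet. The protocol does intend age-matching for HVs, and a missing procedure does not show that matching will fail. Ages and per-subject uptake are listed, so an adjusted analysis could be done later. All of this stands, and it limits the point to the size of the estimated differences.

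A reader might infer that the plan has an inflated false-positive rate. A two-group ET versus HV test with no true difference would reject in 7.1% to 10.8% of trials at a 5-year gap and 13% to 29% at 10 years (SD 15% to 25%). The documents do not support that reading: SAP 8.2 names no pairwise test, and both the gap and the SD are assumed. A reader might also infer that a 5 to 10 year gap is expected, but no document gives ages by group.

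What the reply does not remove is that the secondary endpoint relates uptake to diagnosis, that matching HVs would not align PS with ET, and that an adjustment chosen after seeing the ages is weaker than one fixed beforehand.

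**Conclusion.** The point holds as a minor, essentially free improvement. The model omits a baseline variable that the protocol itself says affects uptake, in a non-randomised comparison with no stated means of balancing age. At gaps of 1 to 2 years the effect is negligible. At 5 to 10 years it would be a noticeable part of the uncertainty in the ET versus HV difference and a modest part of a large PS deficit. That PS has such a deficit is itself an inference: protocol section 4 describes 50% to 80% neuron loss by symptom onset, but no document gives uptake means. The shift of 0.55% per year rests on the cited slope carrying over to the ratio; the size and direction of any gap are unknown. Sensitivity and specificity are unaffected. The unlisted ANOVA groups and the unstated HV matching procedure are missing detail and do not make the point more serious.

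**What to change.** In SAP 8.2, prespecify for each region of interest an ANCOVA of uptake ratio on diagnosis group (PS, ET, HV) plus continuous age. Report age-adjusted group means and differences with 95% CIs, and keep the unadjusted summaries beside them.

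Because the slope may differ in PS, choose one of two options in advance: give PS its own age slope and report differences involving PS at a stated age (for example 60, the midpoint of 40 to 80), or keep a common slope and report the group-by-age interaction descriptively. Do not let an interaction test choose the model: that would add a data-dependent step, with only 20 HVs. Step 6 favours the separate slope.

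Record the change in SAP 11. A sentence on how HVs are age-matched would also help. The cost is SAP wording and one or two model terms; age is already collected at screening (protocol 10.4.1), and no extra subjects or visits are needed.

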10.2.3 Image interpretation and correlation with standard of truth

Anonymised DaTSCANTM SPECT images will be presented in randomized order to 3 independent readers. Each blinded image reviewer will determine if the image is of sufficient quality to be interpretable. If the image is not interpretable, the blinded image reviewer will be required to specify the reason why on the CRF. If the image is considered evaluable by the reader, then the reader will be required to record his/her assessment of the subject's image in terms of a normal pattern of tracer uptake (negative image interpretation) or an abnormal pattern of tracer uptake (positive image interpretation). If the image is classified as abnormal, he/she will be asked to further classify the image as typical SDD or atypical SDD.

The BIE readers will evaluate the DaTSCANTM SPECT images according to the following classification:

- 1. Normal DaTSCANTM SPECT images: 2 symmetric comma- or crescent-shaped focal regions of activity mirrored about the median plane. Striatal activity is distinct, relative to surrounding brain tissue
- 2. Abnormal DaTSCAN™ SPECT image type 1: Activity is asymmetric (i.e., activity in the region of the putamen of 1 hemisphere is absent or greatly reduced with respect to the other). Activity is still visible in the caudate nuclei of both hemispheres, resulting in a comma or crescent shape in 1 and a circular or oval focus in the other. There may be reduced activity between ≥1 striatum and surrounding tissues
- 3. Abnormal DaTSCANTM SPECT image type 2: Activity is absent in the putamen of both hemispheres and confined to the caudate nuclei. Activity is relatively symmetric and forms 2 roughly circular or oval foci. Activity of one or both is generally reduced.
- 4. Abnormal DaTSCANTM SPECT image type 3: Activity is absent in the putamen of both hemispheres and greatly reduced in one or both caudate nuclei. Activity of the striata with respect to the background is reduced.
- 5. Other: Abnormal pattern, not conforming to any of the patterns above, to be specified by the reviewer (e.g., 'punched-out' lesion such as caused by an ischaemic stroke) or if the image cannot be interpreted.

Where an image cannot be assigned to one of the categories 1) to 5) a reason must be specified in the CRF.

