2.2. Secondary Objectives

- To assess the striatal uptake of [¹²³I]ioflupane in healthy Chinese volunteers (no SDD).
- To assess safety parameters (haematology, biochemistry and urinalysis, and vital signs) and the adverse event (AE) profile in Chinese patients/HVs after a single IV administration of DaTSCANTM ioflupane (¹²³I) injection.

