3.2.2. Secondary Endpoints

- Central read (by semi-quantitative assessment by use of DaTQUANTTM) of DaTSCANTM SPECT images to compare specific uptake with clinical diagnosis.
- Comparison and assessment of safety parameters and AEs reported by all study participants.

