4.3. Sample Size Determination

The null hypothesis tests are given as H_0 : $p \le p_0$ where p_0 is the specified threshold. The alternate hypothesis is given by H_a : $p > p_0$. The parameter p represents the sensitivity/specificity of the blinded independent read of DaTSCANTM SPECT images in detecting or excluding SDD, using the clinical diagnosis as established by the investigator as the standard of truth.

An exact binomial test with a nominal 0.05 1-sided significance level will have 80% power to detect the difference between the null hypothesis diagnostic sensitivity threshold of 0.85 and the assumed alternative proportion of 0.95 when the sample size is 59 subjects with SDD present.

An exact binomial test with a nominal 0.05 1-sided significance level will have 80% power to detect the difference between the null hypothesis diagnostic specificity threshold of 0.85 and the assumed alternative proportion of 0.95 when the sample size is 59 subjects with SDD absent.

An extensive set of values for the specified threshold, p_0 , and the resultant sample size (for either sensitivity or specificity) are as follows: $P_0 = 0.89$: n=128; $P_0 = 0.88$: n=107; $P_0 = 0.87$: n= 89;

 $\begin{array}{l} P_0=0.86; \ n=73; \ P_0=0.85; \ n=59; \ P_0=0.84; \ n=55; \ P_0=0.83; \ n=44; \ P_0=0.82; \ n=41; \\ P_0=0.81; \ n=39; \ P_0=0.80; \ n=30. \end{array}$

However, according to regulatory guidelines sample size for a new product with more than 1 indication (which is the case for DaTSCANTM) requires a minimum of 60 pairs of cases. Therefore, the final number of evaluable diseased individuals will be 60 in each group (SDD present and absent).

In addition to the 120 evaluable subjects (subjects with movement disorder), each centre will be requested to recruit 2 to 4 HVs (subjects without movement disorder) for the sole purpose of the creation of a normal database. A total of 20 HVs will be recruited across the centres. These subjects will also be included in the safety analysis.

On the basis of a previous study (DP008-003), it is projected that evaluable results will be obtained for 80% of diseased individuals and 90% of HVs. After adjustment for losses, it is therefore expected that 150 subjects with movement disorders (with or without SDD) and 22 HVs will be needed to provide at least the minimum required number of evaluable subjects.

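### SAP 8.2 plans only an omnibus ANOVA for each uptake ratio; it should also report named group differences with confidence intervals from group-specific variances

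*SAP*

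**What the plan says.** The secondary endpoint in SAP 3.2.2 is a central semi-quantitative read of "SPECT images to compare specific uptake with clinical diagnosis". SAP 8.2 implements it for six regions (left and right striatum, caudate and putamen), each normalised to the occipital cortex. The values "will be summarized with descriptive statistics for each category of subjects with SDD, ET, and HV". Then, for every ratio, "an analysis of variance (ANOVA) will be carried out to test for differences in the striatal uptake ratios among the clinical diagnosis groups". The section ends by promising a listing of the individual values.

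Neither SAP 8.2 nor protocol 12.5.2.1 names a contrast, a confidence interval, a variance assumption or a significance level for this test. Protocol 12.8 states that no power analysis was done for secondary variables.

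The grouping differs between the documents. Protocol 12.5.2.1 summarises "each category of subjects with SDD (PD, MSA, or PSP) and each category of subjects without SDD (ET and HVs", which is up to five categories, whereas SAP 8.2 refers to SDD, ET and HV. SAP 11 declares no change from the protocol's statistical section.

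On numbers, SAP 4.3 says that "the final number of evaluable diseased individuals will be 60 in each group (SDD present and absent". It adds 20 HVs, recruited "for the sole purpose of the creation of a normal database".

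**The concern.** An omnibus F-test asks only whether all group means are equal. One very different group settles it, whatever the others do. Protocol 10.2.3 gives reason to expect such a group: in abnormal image type 2, "Activity is absent in the putamen of both hemispheres and confined to the caudate nuclei". A small p-value for each region would then be close to inevitable. It would neither size the separation of PS from ET nor show whether ET uptake resembles healthy uptake.

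A second, conditional problem follows. Someone wanting those comparisons would naturally take them from the fitted ANOVA, whose default error term pools the variance over all groups. If the SDD group has a different spread, that term is wrong for ET versus HV, and the small HV group makes the comparison imprecise in any case. At stake is how well the semi-quantitative results can be interpreted, not the trial's success rule.

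**Working it through.** **The plan's own figures.** None is given for the ANOVA. The only sample-size figure is for the primary endpoints (SAP 4.3): exact binomial, 0.85 versus 0.95, one-sided 0.05, 80% power. It reproduces: n = 59 with success at 55 or more gives alpha 0.0469 and power 82.8%, whereas n = 58 gives 67.0%.

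**Inputs.** From SAP 4.3: 60 SDD (PS), 60 ET, 20 HV. Assumed, because the documents give no means or SDs: ET and HV share one SD, set to 1; the SDD SD is *r*, from 0.3 to 2; the SDD deficit is *d*, in units of the ET/HV SD; tests are two-sided at 5%; values are normal.

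**1. How large might the deficit be?** Suppose the ratio separated PS from ET as well as the visual read is assumed to (equal-variance binormal). Then *d* = 2 × z(accuracy). At 85%, 2 × 1.036 = 2.1 SD. At 95%, 2 × 1.645 = 3.3 SD.

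**2. Does the omnibus test then tell us anything?** Simulated rejection at 5% with ET and HV equal, for *r* from 0.5 to 2:

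| Deficit *d* (SD) | Rejection |
|---|---|
| 0.25 | 11% to 35% |
| 0.5 | 34% to 92% |
| 1 | 91% to 100% |
| 1.5 | 99.9% to 100% |
| 2 or 3 | 100% |

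At *d* = 2 essentially all runs also gave p < 0.001. The outcome is settled in advance from about 1.5 SD upward, but not at 0.5 SD.

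**3. Pooled error, if contrasts were taken from the ANOVA.** The expected pooled variance is

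s² = (59r² + 59 + 19) / 137.

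- At *r* = 0.3: (5.31 + 78) / 137 = 0.608, so s = 0.78.
- At *r* = 2: (236 + 78) / 137 = 2.292, so s = 1.51.

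The true SD for ET-HV is 1, so its standard error is multiplied by s. The approximate true error of the nominal 5% test is 2 × P(Z > 1.977 s). At *r* = 0.3 this is 2 × P(Z > 1.54) = 12%. At *r* = 2 it is 2 × P(Z > 2.99) = 0.3%. Simulation agrees closely:

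| *r* | s | ET-HV true error, pooled (simulated) | PS-ET: pooled SE / true SE |
|---|---|---|---|
| 0.3 | 0.78 | 13% | 1.06 |
| 0.5 | 0.82 | 10.9% | 1.04 |
| 0.67 | 0.87 | 8.8% | 1.03 |
| 1 | 1.00 | 4.8% | 1.00 |
| 1.5 | 1.24 | 1.5% | 0.97 |
| 2 | 1.51 | 0.3% to 0.4% | 0.96 |

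The last column is s√(2/60) / √((r² + 1)/60). It stays near 1 because the two groups are equal in size. For PS-HV the corresponding ratio runs from 0.91 (*r* = 0.5) to 1.14 (*r* = 2). A Welch test of ET versus HV holds about 5% throughout.

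**4. Precision available for ET-HV.** At an assumed SD of 0.20, the standard error is 0.20 × √(1/60 + 1/20) = 0.052, giving a 95% half-width of about 0.10. Welch power is about 20% for a 0.3 SD difference, 47% for 0.5 SD and 78% for 0.73 SD.

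**The case against.** The other side has a good deal in its favour.

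- **The ANOVA does answer its literal question**, which is whether uptake differs among diagnosis groups. A reader might infer that the secondary analysis cannot answer its question at all. The documents do not support that. Moreover, group means and SDs are reported for every region, and a reader could compute differences and Welch intervals from them.
- **ET versus HV is not a stated objective.** The HV objective in SAP 2.2 is to assess uptake in healthy volunteers, which is an estimate rather than a comparison, and the HVs are there to build a normal database. The distorted ET-HV error therefore belongs to a contrast that the SAP does not contain.
- **Not every contrast is affected.** A reader might infer that any contrast from the ANOVA would have wrong error bars. PS-ET, the comparison closest to the diagnostic question, is almost unaffected.
- **Unequal spread is assumed.** The documents give no SDs, and SAP 8.2 does not specify equal variances; that is only the usual default. The direction of error reverses with the assumption, and at *r* = 1 there is no error.
- **The large deficit is also assumed.** Image type 1 in protocol 10.2.3 keeps caudate activity visible on both sides, so near-certain rejection need not extend to all six regions.

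All of this stands, and it limits the point to an improvement. It does not supply what is missing: a pre-specified estimate and interval for any group difference. Leaving readers to derive these from tables is a weaker plan than naming them.

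**Conclusion.** The point holds as a modest one. The inferential part of SAP 8.2 is a single omnibus test per region, which gives neither the size nor the precision of any difference. Its near-certain rejection rests on a deficit of about 1.5 SD or more; the 2.1 to 3.3 SD benchmark carries the assumed visual-read accuracy over to the uptake ratios.

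The error-rate figures are doubly conditional: on someone later taking contrasts from a pooled-variance fit, and on an SDD spread that differs from the others. Within the assumed SD ratios of 0.3 to 2, the effect is serious only for ET-HV, moderate for PS-HV and small for PS-ET. Since the direction is unknown in advance, a method that does not depend on it is preferable.

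The difference in grouping between protocol and SAP is a fact of the text and needs settling in any case. None of this touches sensitivity, specificity or the reader-based success rule in SAP 8.1.

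**What to change.** In SAP 8.2:

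1. Keep the ANOVA if wanted, but make the reported inference the mean differences PS-ET, PS-HV and ET-HV for each region, each with a 95% confidence interval from group-specific variances (Welch, or a model with a separate residual variance per group).
2. State the groups consistently with protocol 12.5.2.1: say whether PD, MSA and PSP are separate or combined as PS for the ANOVA and for the differences, and record any departure in SAP 11.
3. Optionally, add the area under the ROC curve with its interval for PS versus ET.

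The cost is SAP wording, a few lines of code and slightly longer output; no new data are needed. The ET-HV interval will be fairly wide because there are only 20 HVs. A wide interval that includes zero should not be read as showing that ET and healthy uptake are the same.
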